4.1.3.6 Dose reduction

If patients develop a DLT or a DLT-equivalent adverse event, the study treatment will be resumed at a reduced dose after the DLT or the DLT-equivalent adverse event has recovered to baseline or CTCAE grade ≤1. However, study treatment should not be resumed and the patient should discontinue the study treatment if any of the criteria in Section 3.3.4 are met.

Only 2 dose reductions will be permitted according to Table 4.1.3.6: 1. If dose reductions are required 3 times throughout the study treatment or dose reduction less than 500 mg, the patient should be discontinued the study treatment.

Table 4.1.3.6: 1 Dose reduction scheme

Starting dose	Assigned dose after the first dose reduction	Assigned dose after the second dose reduction
750 mg	500 mg	Patient discontinuation
1000 mg	750 mg	500 mg
1400 mg	1000 mg	750 mg

4.1.3.7 Dose interruption

The study treatment in a patient may be interrupted at any time when there is concern about the patients' safety after discussion and agreement with the investigator and the sponsor. In

Proprietary confidential information © 2024 Boehringer Ingelheim International GmbH or one or more of its affiliated companies

case patients develop a DLT or a DLT-equivalent adverse event, see [Section 4.1.3.6](#) for details.

During drug interruption, the scheduled BI 836845 administration will be missed and will not be retrospectively administered. All the other scheduled assessments shall be performed as described in the [Flow Chart](#). Patients should discontinue the study treatment when the duration of dose interruption exceeds 4 weeks as counted from the next planned treatment administration according to [Section 3.3.4.1](#).

4.1.3.8 Initiation of rollover part

At the time of all patients in the trial having sufficient data to answer the primary endpoint (see [Section 5.2.1](#)), patients continuing on study treatment will have the EOT assessments (except for blood collection for biomarker analyses) performed and then continue on study treatment into the rollover part with reduced clinical data collection.

The investigator should make efforts to keep administration of BI 836845 at intervals of 7 days. However, weekly administration schedule can temporarily be accelerated, delayed or skipped due to administrative reasons at the discretion of the investigator.

4.1.4 Drug assignment and administration of doses for each patient

A method of drug assignment for patients is described in [Section 4.1.2](#).

BI 836845 will be administered intravenously over 1 hour with repeated administration weekly until patients meet any of criteria for discontinuation (see [Section 3.3.4](#) for definition) as per the Flow Chart. Infusion duration on Day 1 of Cycle 1 may be extended to over 1 hour and up to a maximum of 3 hours in cases of CTCAE grade ≥ 2 infusion reactions (see [Section 4.2.1.1](#) for grading and management of infusion reactions). **An infusion duration of less than 1 hour must be avoided because mannitol is used in the formulation of BI 836845.**

Patients will be treated at the assigned dose during the study treatment unless patients are required the dose reduction (see Section 4.1.3.6 for definition). Intra-patient dose escalation will not be allowed.

In case of a delay of infusion, the reason and the exact time of deviation must be recorded in the eCRF because the accuracy of this information is crucial for the proper evaluation and appraisal of pharmacokinetics and other data. In case of a drug interruption, the reason must be recorded in the eCRF. Administration status is not recorded in the eCRF during the rollover part.

4.1.5 Blinding and procedures for unblinding

4.1.5.1 Blinding

Not applicable because it is an open-label trial

4.1.5.2 Procedures for emergency unblinding

Not applicable because it is an open-label trial

4.1.6 Packaging, labelling, and re-supply

BI 836845 drug supplies will be provided from [REDACTED]

For details of packaging and the description of the label as well as the process for resupply of investigational drug, see the ISF.

4.1.7 Storage conditions

BI 836845 will be stored in the original packaging at the temperature stated on the drug label.

4.1.8 Drug accountability

Drug supplies which will be provided by the sponsor must be kept in a secure and limited access storage area in the hospital pharmacy. Where necessary, a temperature log must be maintained to make certain that the drug supplies are stored at the correct temperature according to the ISF.

The investigational drug storage manager will receive the investigational drugs delivered by the sponsor when the following requirements are fulfilled:

- Approval of the CTP by the Institutional Review Board (IRB)
- Availability of a signed and dated clinical trial contract between the sponsor and the Head of Trial Centre
- Approval/notification of the regulatory authority, e.g. competent authority
- Availability of the curriculum vitae of the principal investigator
- Availability of a signed and dated CTP or immediately imminent signing of the CTP

The investigational drug storage manager must maintain records of the product's delivery to the trial site, the inventory at the trial site, the use by each patient, and the return of unused products.

These records will include dates, quantities, batch/serial numbers, expiry ('use-by') dates, and medication numbers. The investigational drug storage manager will maintain records that document adequately that the patients were provided the doses specified by the CTP and reconcile all investigational products received from the sponsor.

At the time of return of unused products, the investigational drug storage manager must verify that all unused drug supplies have been returned.

Upon completion of the trial, the investigational storage manager submits to the sponsor a copy of the investigational drug dispensing and return log. When submitting the copy, the investigational drug storage manager should exercise caution to preserve the anonymity of patients' names.

4.2 CONCOMITANT THERAPY, RESTRICTIONS, AND RESCUE TREATMENT

4.2.1 Rescue medication, emergency procedures, and additional treatments

Rescue medication to reverse the effects of BI 836845 is not available. Potential side effects of BI 836845 should be treated symptomatically.

Symptomatic treatments of tumour-associated symptoms are allowed. Concomitant medications and/or concomitant therapies to provide adequate supportive care may be given as clinically necessary. Patients should receive full supportive care including transfusions of blood and blood products, antibiotics, analgesia etc., according to local practice or guidelines where appropriate. Anti-emetic medication should be prescribed according to local practice.

Precaution should be taken to avoid extravasation. Patients should be asked to report any pain or burning at the site of injection immediately. If extravasation is suspected, the infusion should be stopped immediately. Treatment should be initiated according to local practice.

All concomitant and concomitant therapies should be recorded in the eCRF except during the rollover part. Trade name and indication of concomitant therapies will be documented. If patients receive parenteral nutrition during the trial, the components need not be specified in detail and should just be indicated as "parenteral nutrition" and the form be completed. If a patient requires anaesthesia, it will be sufficient to indicate "anaesthesia" without specifying the details.

If surgery is considered necessary for the patient, whenever possible, at least 7 days should elapse after the last dose of BI 836845 before surgery is performed. Treatment can be resumed from 12 days after surgery.

4.2.1.1 Management and grading of infusion reactions

The investigational drug infusions should always be administered in a hospital environment and under close supervision of the medically qualified staff member with immediate availability of full resuscitation facilities.

Infusion reactions may occur during infusion with BI 836845 and include pyrexia, chills, rigors, dyspnoea, urticaria, bronchospasm, hypotension, and hypertension. **A 1-hour observation period is recommended following each infusion.** Mild to moderate infusion reactions may be managed with a slower infusion rate and prophylactic antihistamines for subsequent dosing. Severe reactions require immediate interruption of infusion. The details are summarised in Table 4.2.1.1: 1. The grading of hypersensitivity reactions will be according to CTCAE version 4.03.

Table 4.2.1.1: 1 Infusion reaction management

Intensity for infusion reaction	Management
CTCAE grade 1 or 2	In the event of a mild to moderate CTCAE grade 1 or 2 non-allergic infusion reaction, the infusion rate should be reduced by 50%. Once the adverse event has resolved, the investigator should wait and deliver the infusion at the reduced rate for another 30 minutes. If tolerated, the infusion rate may then be increased to the next close rate on the patient's infusion schedule. In case of a CTCAE grade 2 adverse event that requires therapy (e.g. antihistamines, nonsteroidal anti-inflammatory drugs [NSAIDs], steroids, narcotics, intravenous fluids) or infusion interruption and resolves promptly the infusion may also be restarted at half of the infusion rate at the time of onset of the infusion reaction.
CTCAE grade 3	For Patients experiencing CTCAE grade 3 infusion reaction, infusion should be interrupted immediately and patients should receive aggressive symptomatic treatment. Only after all the symptoms have disappeared the infusion should be started. The infusion rate at restart should be half of the infusion rate at the time of onset of the infusion reaction.
CTCAE grade 4	For patients experiencing CTCAE grade 4 infusion reaction such as anaphylaxis during an infusion should have infusion immediately stopped and receive appropriate treatment including use of resuscitation medications and/or equipment that must be available. Such patients should be discontinued the study treatment and should be followed up.

The infusion reactions should be treated symptomatically as judged clinically relevant by the investigator. For symptomatic treatment of infusion reactions: hydrocortisone, antihistamines such as chlorpheniramine accompanied by an antipyretic/analgesic, and/or a bronchodilator is recommended.

4.2.1.2 Management of hyperglycaemia

In case of hyperglycaemia treatment should follow standard and local guidelines and may include oral antidiabetics such as metformin. The appropriate expert advice should be considered in the management of hyperglycaemia. When treatment with the investigational drug is discontinued, the need for further antidiabetic treatment has to be evaluated depending on the blood glucose levels of the patient.

4.2.2 Restrictions

4.2.2.1 Restrictions regarding concomitant treatment

The use of concomitant drugs for prophylactic purpose is prohibited to prevent the expression of drug-related adverse events. Additional experimental anti-cancer treatment and/or standard chemotherapy, immunotherapy, hormone treatment, with the exception of megestrol acetate and LHRH analogues, is not allowed during the trial.

For symptom control palliative radiotherapy may be permitted after discussion and agreement with the investigator and the sponsor on a case-by-case basis (e.g. for bone metastases). The impact of any palliative radiotherapy on tumour assessments must be documented.

Any concomitant medication should be reduced to the clinically necessary minimum on the days of BI 836845 infusion.

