The potential risks associated with BI 836845 are unknown in Japanese patients and unexpected or infrequent adverse events may occur in the clinical trial. The proposed trial will evaluate stepwise dose escalation of BI 836845, and the investigator should carefully be monitored the patients' safety during trial participation.

Although BI 836845 is a fully human antibody given intravenously, there may be potential for infusion reactions (e.g. infusion-related reactions, injection site reactions, immune system disorders) to occur. Such infusion reactions will be graded thoroughly and appropriate preventative and/or corrective actions implemented following the standard of care for such adverse events.

Although rare, a potential for drug-induced liver injury (DILI) is under constant surveillance by sponsors and regulators. Therefore, this study requires timely detection, evaluation, and follow-up of laboratory alterations of selected liver laboratory parameters to ensure patients' safety.

Together with the encouraging preliminary signs of anti-tumour activity observed (see Section 1.4 for details), this 1280.15 trial had warranted, until the negative efficacy results for BI 836845 in the placebo-controlled randomised Phase II 1280-0022 trial, continuation of clinical investigation of BI 836845 in patients with solid tumours. The 1280-0022 Phase II placebo-controlled, randomised trial recently completed primary endpoint analysis and showed no added benefit of BI 836845 compared to placebo, in patients with everolimus and exemestane backbone therapy, when treating trial participants with metastatic breast cancer, HR+, HER2- and non-visceral disease. No new safety signals were observed with the addition of BI 836845 to the everolimus and exemestane combination.

In consideration of these topline results of 1280-0022, as of 19 October, 2021, Boehringer Ingelheim recommended to immediately discontinue all BI 836845 treatments. As a consequence of the worsening in benefit-risk for BI 836845, Boehringer Ingelheim also

Proprietary confidential information © 2024 Boehringer Ingelheim International GmbH or one or more of its affiliated companies

decided to terminate all oncology drug development for BI 836845 including the cessation of further manufacturing of investigational medicinal product BI 836845.

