3. DESCRIPTION OF DESIGN AND TRIAL POPULATION

3.1 OVERALL TRIAL DESIGN AND PLAN

This trial is an open-label dose escalation phase I trial of BI 836845 in Japanese patients with various types of advanced solid tumours to identify the MTD, safety, pharmacokinetics, pharmacodynamics, and preliminary anti-tumour activity of BI 836845. Patients will be administered BI 836845 weekly and continued the study treatment every 21 days without discontinuation of study treatment.

Patients will be enrolled into the study at the time of obtaining written informed consent and will subsequently be assessed for the eligibility within a maximum 28 days screening period. Study treatment will be started after the investigator confirms the eligibility for the study treatment from Cycle 1 and will be continued until patients meet any of criteria for discontinuation, e.g. progressive disease (PD), undue toxicity, consent withdrawal (see [Sections 3.3.4.1](#) and [3.3.4.2](#) for definition). One treatment cycle consists of 21 days. End of treatment (EOT) visit will be conducted within 5 days after patient discontinuation of study treatment. If patient discontinuation of study treatment falls on a scheduled visit, EOT visit should be conducted instead of assessments at the scheduled visit. Follow-up period will stop when once a patient has disease progression, is dead, is lost to follow-up, or has treatment with another anti-cancer drug, whichever occurs first, or patients have been willing to discontinue the trial. All adverse events will be collected and followed up according to [Section 5.2.2.2](#).

At the time of all patients in the trial having sufficient data to answer the primary endpoint (see [Section 5.2.1](#)), patients continuing on study treatment will have the EOT assessments (except for blood collection for biomarker analyses) performed and then continue on study treatment into the rollover part with reduced clinical data collection. Clinical assessments and laboratory tests are not mandatory and appropriately performed as per the standard of care at the study sites or at the discretion of investigator, and only clinical relevant abnormalities are reported as adverse events according to Section 5.2.2.2. Results for the assessments and tests should be recorded in the source data only, additional documentation in the electronic case report form (eCRF) is not required.

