4.1.3.2 Dose-limiting toxicities

For definition of a DLT, it is essential that patients are treated sufficiently according to supportive care standards, and baseline conditions, coexisting symptoms, and/or transient laboratory abnormalities of patients are also considered. A drug-related adverse event constitutes a DLT, if one of the following applies during Cycle 1:

Haematological toxicities:

- CTCAE grade 4 neutropenia (neutrophil counts of $<500/\mu\text{L}$) lasting 7 or more days
- Febrile neutropenia (neutrophil counts of $<1000/\mu\text{L}$ with once observed a temperature of $\geq38.3^\circ\text{C}$ or a sustained temperature of $\geq38.0^\circ\text{C}$ for more than 1 hour)
- Infection with neutrophil counts of $<1000/\mu\text{L}$
- CTCAE grade 4 thrombocytopenia (platelet counts of $<25\,000/\mu\text{L}$) or CTCAE grade 3 thrombocytopenia (platelet counts of $<50\,000\text{--}25\,000/\mu\text{L}$) associated with bleeding requiring platelet transfusion

Non-haematological toxicities:

- CTCAE grade 3 or 4 non-haematologic toxicity (except incompletely treated nausea, untreated vomiting, untreated diarrhoea, skin toxicity, fatigue, infusion reaction, electrolyte, hyperglycaemia, AST, or ALT). The following drug-related non-haematological toxicities should be defined as DLTs:
 - CTCAE grade ≥ 2 infusion reaction despite adequate pre-medication
 - CTCAE grade ≥ 2 nausea and/or vomiting persisting for 7 or more days despite antiemetic treatment
 - CTCAE grade ≥ 3 skin toxicity despite adequate supportive care measures for up to 14 days if it does not reach an improvement to grade ≤ 2
 - CTCAE grade ≥ 3 hyperglycaemia resistant to treatment with anti-diabetic agents
 - Any electrolyte CTCAE grade 3 adverse event which is refractory to optimal correction therapy
 - No recovery from a non-DLT CTCAE grade ≥ 3 toxicity to grade ≤ 1 within 14 days of administered dose
 - Sustained CTCAE grade 3 fatigue or asthenia for longer than 96 hours associated with deterioration of ECOG performance status

It is understood that also other drug-related adverse events (CTCAE grade 2) may carry the potential to be significant enough to necessitate treatment interruption or discontinuation, and as such qualify as DLT. Such adverse events will be required the confirmation after thorough discussion between the investigator and the sponsor on a case-by-case basis.

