	C3	Infusion time for the investigational treatment outside of CTP specific boundaries	Check medical review of administration data. Total infusion time (allowing for interruptions) $<$ 60 minutes See the section 4.3 in CTP.	None
	C4	Patient assignment not followed	Patients do not receive the initial treatment they were allocated to	None

Table 6.2:1 (continued)

Important protocol deviations

Proprietary confidential information © 2018 Boehringer Ingelheim International GmbH or one or more of its affiliated companies

Category/ Code		Description	Requirements	Exclude d from
D [2]		Concomitant medication		
	D1	Prohibited treatment during trial conduct phase	Indicated by medical review of concomitant therapy use during study treatment according to section 4.2.2.1 in CTP. Discuss the list which is given by TCM during MQRM.	None
E [2]		Missing Data		
	E1	Imaging assessments not done according to CTP instructions	Imaging assessment should be performed at Screening and several time points thereafter (see table 6.7.2: 1).	None
	E2	Pregnancy test not done according to CTP instructions	Exclusion criteria EX16 or Pregnancy test missing.	None
F [2]		Trial Specific protocol deviations		
	F1	Other protocol deviations affecting patient rights or safety	Manual PVs can be collectively captured	None

[1] iPD will be derived automatically

[2] iPD will be identified via individual review at MQRM/RPM/DBL.

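### Protocol 4.2.2.1 bans prophylaxis without exception while 4.2.1.1 permits prophylactic antihistamines after an infusion reaction, and the infusion-reaction DLT criterion depends on pre-medication

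*Protocol*

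**What the plan says.** Protocol 4.2.2.1 (Restrictions regarding concomitant treatment): "The use of concomitant drugs for prophylactic purpose is prohibited to prevent the expression of drug-related adverse events". No reaction type, patient group or cycle is exempted.

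Protocol 4.2.1.1 (Management and grading of infusion reactions): "Mild to moderate infusion reactions may be managed with a slower infusion rate and prophylactic antihistamines for subsequent dosing".

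Protocol 2.3 (Benefit–risk assessment) foresees, for infusion reactions, "appropriate preventative and/or corrective actions implemented following the standard of care for such adverse events".

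Protocol 4.1.3.2 (Dose-limiting toxicities) takes infusion reaction out of the general grade 3 or 4 non-haematological criterion; the exception list ends "fatigue, infusion reaction, electrolyte, hyperglycaemia, AST, or ALT". It then lists, at grade 2 or higher, "infusion reaction despite adequate pre-medication" as a DLT. The window is set by "A drug-related adverse event constitutes a DLT, if one of the following applies during Cycle 1".

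SAP 6.2, Table 6.2:1, code D1 (prohibited treatment) is to be identified as follows: "Indicated by medical review of concomitant therapy use during study treatment according to section 4.2.2.1 in CTP". The table excludes no patient from analysis for D1.

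**The concern.** An antihistamine given before Day 8 because of a Day 1 reaction is permitted by one section and prohibited by another. Nothing in the protocol ranks the two sections or limits the ban to patients who have not yet reacted.

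In many trials this would be a drafting matter. Here pre-medication is part of the definition of a DLT, and the DLT count determines the MTD. The same grade 2 reaction at a later Cycle 1 infusion can meet the listed criterion or fail to meet it, depending on which section the physician relied on. The MTD, or the tolerability statement at 1400 mg, would then rest on a condition (with or without prophylaxis) that the planned output does not show.

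**Working it through.** **The plan's own figures.** Three dose cohorts of at most 6 give 3 × 6 = 18 evaluable patients, and 18 + 6 = 24 with the expansion cohort. Both match the protocol, and this point does not change them.

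**Inputs.**
- Ban on prophylaxis: Protocol 4.2.2.1.
- Permission after a reaction: Protocol 4.2.1.1.
- DLT criterion and Cycle 1 window: Protocol 4.1.3.2.
- Weekly dosing in a 21-day cycle, infusions on Days 1, 8 and 15: Protocol 3.1 and Flow Chart.
- MTD limit of at most 1 of 6 evaluable patients with a DLT: Protocol 4.1.3.3.

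**Which infusions are affected.** Section 4.2.1.1 provides prophylaxis only for infusions after a reaction, so Day 1 is the same under both sections. The conflict can arise on Days 8 and 15, which lie inside the DLT window, and only for patients who have already reacted.

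**One patient under each section.** Suppose a grade 1 reaction on Day 1 and a grade 2 reaction on Day 8.

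| | 4.2.2.1 followed literally | 4.2.1.1 option used |
|---|---|---|
| Antihistamine before Day 8 | No | Yes |
| Listed infusion-reaction DLT criterion on Day 8 | Not met | Can be met, if the antihistamine is accepted as adequate |
| Case-by-case route for other grade 2 events | Could still make it a DLT | Not needed |
| SAP code D1 | Nothing to list | Could be listed |

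**Effect on the decision.** If one other patient in a cohort of 6 has a DLT, the count is 1/6 (16.7%) when this patient is not counted and 2/6 (33.3%) when counted. The first meets the MTD limit and the second exceeds it.

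**The opposite effect.** The antihistamine may also prevent the Day 8 reaction, leaving no event to count. The documents give no rates, so the following only illustrates sensitivity, under assumed DLT probabilities. With probability p for every patient,

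P(at most 1 of 6) = (1 − p)^6 + 6p(1 − p)^5.

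- p = 0.30: 0.1176 + 0.3025 = 0.420.
- p = 0.10: 0.5314 + 0.3543 = 0.886.
- Three patients at 0.10 and three at 0.30: P(0) = 0.9³ × 0.7³ = 0.2500; P(1) = 3 × 0.1 × 0.9² × 0.7³ + 0.9³ × 3 × 0.3 × 0.7² = 0.0833 + 0.3215 = 0.4048; sum 0.655.

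Chance of meeting the limit, by number of patients pre-medicated:

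| Assumed DLT risk without → with pre-medication | 0 of 6 | 3 of 6 | 6 of 6 |
|---|---|---|---|
| 20% → 10% | 0.655 | 0.778 | 0.886 |
| 30% → 10% | 0.420 | 0.655 | 0.886 |
| 40% → 20% | 0.233 | 0.415 | 0.655 |

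These figures overstate the exposure: they apply the lower risk to the whole of Cycle 1, whereas only re-infused reactors are affected. They also assume that reactions count alike with and without pre-medication, which is the matter in dispute.

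**The case against.** A reader might infer that a site cannot comply with both sections. That is too strong. Section 4.2.1.1 is permissive, so a site that slows the infusion and gives no antihistamine breaches neither. The conflict arises only when the option is used.

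A coherent reading also exists: the ban covers prophylaxis before any reaction, and 4.2.1.1 is a specific provision for patients who have reacted. This is reasonable, but neither document states it and D1 does not reflect it. Section 2.3 settles nothing, because it names no drug and a slower infusion can itself be preventative.

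Safeguards reduce the risk of arbitrary classification. Section 4.1.3.2 lets other significant grade 2 events qualify as DLTs case by case, every DLT must be agreed between investigator and sponsor, an external expert is assigned (3.1.1), and there is one trial site (3.3). These stand. They mean that the Day 8 reaction without an antihistamine is not necessarily a non-DLT, but it would then count by discretion and not by the listed criterion.

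A reader might also infer that D1 removes patients from the analysis. It does not. SAP 6.2 calls the table a working list, D1 is identified by individual review, and nobody is excluded. The harm is a misleading label.

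Finally, a mixed cohort would remain if the reconciled rule allowed prophylaxis after a reaction. This is correct, and it is why rewording alone is not enough and the output must show pre-medication status.

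**Conclusion.** The contradiction stands and should be resolved. Using the option in 4.2.1.1 breaches 4.2.2.1 as written. Because the listed criterion requires pre-medication, a literal ban leaves it almost impossible to meet, while the 4.2.1.1 option makes it attainable on Days 8 and 15.

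The effect is confined to patients who react and are infused again in Cycle 1, and mainly to infusion-reaction DLTs. One such patient can move a cohort of 6 across the MTD limit, assuming that exactly one other patient has a DLT, that the antihistamine is accepted as adequate, and that the case-by-case route is not used for the patient without it.

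A reader might infer that the MTD is biased in a known direction. The documents do not support that: pre-medication can make a reaction countable and can also prevent it, and no rates are given.

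**What to change.** 1. Reconcile Protocol 4.2.2.1, 4.2.1.1 and 4.1.3.2 so that one rule states whether and when prophylaxis for infusion reactions is permitted, and how the DLT criterion applies to infusions given with and without it. Which rule to adopt is for the sponsor to decide.
2. Align SAP Table 6.2:1, code D1, with that rule.
3. In the SAP 7.4 DLT output, show for each Cycle 1 infusion reaction, whether or not it was counted as a DLT, if pre-medication was given at that infusion. The MTD or tolerability statement can then name its condition.

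The cost is a short wording change in the protocol, one SAP table row and one listing column. No new data collection is foreseen: Protocol 4.2.1 already records trade name and indication of concomitant therapies outside the rollover part, and SAP 7.2 uses their start and stop dates. The documents do not say whether time of day is recorded, so separating prophylaxis from treatment on an infusion day may rest on the recorded indication. Since Protocol 2.3 reports that development has ended, items 2 and 3 carry most of the remaining value, for reading the data collected.
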